## **6.7 Intervention After the End of the Study**

There is no study-specified intervention following the end of the study.

## **6.8 Clinical Supplies Disclosure**

The emergency unblinding call center will use the intervention allocation/randomization schedule for the study to unblind participants and to unmask study intervention identity. The emergency unblinding call center should only be used in cases of emergency (see Section 8.1.10). The Sponsor will not provide random code/disclosure envelopes or lists with the clinical supplies.

This study is blinded but supplies are provided open label; therefore, an unblinded pharmacist or qualified study site personnel will be used to blind supplies. Study intervention identity (name, strength, or potency) is included in the label text; random code/disclosure envelopes or lists are not provided.

# **7 DISCONTINUATION OF STUDY INTERVENTION AND PARTICIPANT WITHDRAWAL**

## **7.1 Discontinuation of Study Intervention**

Discontinuation of study intervention does not represent withdrawal from the study.

As certain data on clinical events beyond study intervention discontinuation may be important to the study, they must be collected through the participant's last scheduled follow-up, even if the participant has discontinued study intervention. Therefore, all participants who discontinue study intervention prior to completion of the protocol-specified treatment regimen will still continue to participate in the study as specified in Section 1.3 and Section 8.1.9, or if available, a protocol clarification letter.

Participants may discontinue study intervention at any time for any reason or be discontinued from the study intervention at the discretion of the investigator should any untoward effect occur. In addition, a participant may be discontinued from study intervention by the investigator or the Sponsor if study intervention is inappropriate, the study plan is violated, or for administrative and/or other safety reasons. Specific details regarding procedures to be performed at study intervention discontinuation are provided in Sections 8.1.9.

A participant must be discontinued from study intervention but continue to be monitored in the study for any of the following reasons:

- The participant or participant's legally acceptable representative requests to discontinue study intervention.
- The participant's treatment assignment has been unblinded by the investigator, or through the emergency unblinding call center.
- The participant has a medical condition or personal circumstance which, in the opinion of the investigator and/or Sponsor, placed the participant at unnecessary risk from continued administration of study intervention.
- The participant has a confirmed positive serum pregnancy test.

For participants who are discontinued from study intervention all applicable discontinuation activities will be performed according to Section 8.1.9, or if available, a protocol clarification letter.

Discontinuation from study intervention is "permanent." Once a participant is discontinued from study intervention, they shall not be allowed to restart study intervention.

## 7.2 Participant Withdrawal From the Study

A participant must be withdrawn from the study if the participant or participant's legally acceptable representative withdraws consent from the study.

If a participant withdraws from the study, they will no longer receive study intervention or be followed at scheduled protocol visits.

Specific details regarding procedures to be performed at the time of withdrawal from the study, as well as specific details regarding withdrawal from future biomedical research, are outlined in Section 8.1.9. The procedures to be performed should a participant repeatedly fail to return for scheduled visits and/or if the study site is unable to contact the participant are outlined in Section 7.3.

### 7.3 Lost to Follow-up

If a participant fails to return to the clinic for a required study visit and/or if the site is unable to contact the participant, the following procedures are to be performed:

- The site must attempt to contact the participant and reschedule the missed visit. If the participant is contacted, the participant should be counseled on the importance of maintaining the protocol-specified visit schedule.
- The investigator or designee must make every effort to regain contact with the participant at each missed visit (eg, telephone calls and/or a certified letter to the participant's last known mailing address or locally equivalent methods). These contact attempts should be documented in the participant's medical record.
- Note: A participant is not considered lost to follow-up until the last scheduled visit for the individual participant. The missing data for the participant will be managed via the prespecified statistical data handling and analysis guidelines.

## 8 STUDY ASSESSMENTS AND PROCEDURES

- Study procedures and their timing are summarized in the SoA.
- Adherence to the study design requirements, including those specified in the SoA, is essential and required for study conduct.
- The investigator is responsible for ensuring that procedures are conducted by appropriately qualified (by education, training, and experience) staff. Delegation of study site personnel responsibilities will be documented in the Investigator Trial File Binder (or equivalent).
- All study-related medical decisions must be made by an investigator who is a qualified physician.
- All screening evaluations must be completed and reviewed to confirm that potential participants meet all eligibility criteria. The investigator will maintain a screening log to record details of all participants screened and to confirm eligibility or record reasons for screening failure, as applicable.
- Procedures conducted as part of the participant's routine clinical management (eg, blood count) and obtained before signing of ICF may be utilized for screening or baseline purposes provided the procedure met the protocol-specified criteria and were performed within the time frame defined in the SoA.
- Additional evaluations/testing may be deemed necessary by the investigator and or the Sponsor for reasons related to participant safety. In some cases, such evaluation/testing may be potentially sensitive in nature (eg, HIV, Hepatitis C), and thus local regulations may require that additional informed consent be obtained from the participant. In these cases, such evaluations/testing will be performed in accordance with those regulations.

- The maximum amount of blood collected from each participant over the duration of the study will not exceed 278 mL (Appendix 8).
- Repeat or unscheduled samples may be taken for safety reasons or for technical issues with the samples.

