b. Participants will be confined minimally from Day -6 until Day 11 procedures are complete.

c. Single HR and BP measurements will be obtained at all timepoints unless otherwise noted. On the following days, specific timepoints are noted:

- Day -1 (triplicate measurements): Time-matched to 8, 16 and 24 hours postdose vital signs.
- Day 1, Day 2, Day 3 and Day 9: 8, 16 and 24 hours postdose
- Day 11: Time-matched to 24-hour postdose vital signs

d. Orthostatic assessments in HR and BP will follow semi-recumbent vital sign assessments. Participants should be standing for approximately 2 minutes prior to the orthostatic assessments. Orthostatic HR and BP measurements will be obtained on:

- Day -1: Time-matched to 8, 16 and 24 hours postdose orthostatic vital signs.
- Day 1, Day 2, Day 3 and Day 9: 8, 16 and 24 hours postdose
- Day 11: Time-matched to 24-hour postdose orthostatic vital signs

e. Scheduled assessments are completed predose on dosing days and at any time on non-dosing days.

f. Single 12-lead safety ECG measurements will be taken at all postdose timepoints. On the following days, specific timepoints are noted:

- Day 1: Triplicate measurements within 2 hours prior to dosing
- Day 1, Day 2, Day 3 and Day 9: 8, 16 and 24 hours post-dose

g. Screening UDS is mandatory; any additional UDS are conducted per site SOP. UDS prior to randomization will be done on the day of admission.

h. Additional BARS, AIMS and SAS assessments will be conducted as soon as possible when there are observed or reported complaints of dystonia and/or akathisia (See Section 8.3.6).

i. MK-8189 plasma PK sample collection:

- Day 1 and Day 2: predose, 2, 6, 8, 10, 12 and 16 hours postdose
- Day 3: predose, 2, 6, 8, 10, 12, 16 and 24 hours postdose
- Day 9: predose, 2, 6, 8, 10, 12, 16, 24, 36 and 48 hours postdose
- Optional sample when signs of dystonia and/or akathisia occur.
- Leftover main study plasma will be stored for future biomedical research if the participant consents to future biomedical research.

j. This sample will be drawn for CYP2C9 and for planned analysis of the association between genetic variants in DNA and drug response. If the IRB/IEC does not approve of the planned analysis of the association between DNA variation and drug response, or if there is a local law or regulation prohibiting the same, data analysis will be limited to CYP2C9. Leftover extracted DNA will be stored for future biomedical research.

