## 10.8 Appendix 8: Blood Volume Table

Part 1: All Panels	Pre-study (Screening)	Treatment Periods	Poststudy	Total Collections	mL Per Collection	Total mL/Test
Laboratory Safety Tests including Serum $\beta$ -hCG (WOCBP only) or Serum FSH (WONCBP only)	1	3	1	5	12.5	62.5
HIV/Hepatitis Screen (per site SOP)	1			1	8.5	8.5
Blood for Planned Genetic Analysis		1		1	8.5	8.5
Blood for MK-8189 and/or metabolites assay (Panel A)		26		26	4.0	104.0
Blood for MK-8189 and/or metabolites assay (Panel B)		25		25	4.0	100.0
Blood for MK-8189 and/or metabolites assay (Panel C)		34		34	4.0	136.0
Blood for IV catheter flush (Panel A) a				33	2.0	66.0
Blood for IV catheter flush (Panel B) a				32	2.0	64.0
Total Blood Volume per Participant for Panel A b						249.5 mL
Total Blood Volume per Participant for Panel B b						243.5 mL
Total Blood Volume per Participant for Panel C b						215.5 mL

a If IV catheter use is necessary to support blood collection, additional blood (up to 2 mL per collection) may be collected and discarded prior to drawing the sample.

b If additional pharmacokinetic/pharmacodynamic and/or safety analysis is necessary, additional blood (up to 50 mL) may be obtained.

Part 2: All Panels	Pre-study (Screening)	Treatment Periods	Poststudy	Total Collections	mL Per Collection	Total mL/Test
Laboratory Safety Tests including Serum FSH (Panel D/F)	1	3	1	5	12.5	62.5
Laboratory Safety Tests including Serum FSH (Panel E/G Titration Regimen 1)	1	5	1	7	12.5	87.5
Laboratory Safety Tests including Serum FSH (Panel E/G Titration Regimens 2 & 3)	1	4	1	6	12.5	75.0
HIV/Hepatitis Screen (per site SOP)	1			1	8.5	8.5
Blood for Planned Genetic Analysis		1		1	8.5	8.5
Blood for MK-8189 and/or metabolites assay (Panel D/F and Panel E/G Titration Regimen 3)		34		34	4.0	136.0
Blood for MK-8189 and/or metabolites assay (Panel E/G Titration Regimen 1)		26		26	4.0	104.0
Blood for MK-8189 and/or metabolites assay (Panel E/G Titration Regimen 2)		25		25	4.0	100.0
Blood for IV catheter flush (Panel D/F) a				41	2.0	82.0
Blood for IV catheter flush (Panel E/G Titration Regimen 1) a				35	2.0	70.0
Blood for IV catheter flush (Panel E/G Titration Regimen 2) a				33	2.0	66.0
Blood for IV catheter flush (Panel E/G Titration Regimen 3) a				42	2.0	84.0
Total Blood Volume per Panel D/F Participant b						297.5 mL

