Total Blood Volume per Panel E/G Titration Regimen 1 Participant b						278.5 mL
Total Blood Volume per Panel E/G Titration Regimen 2 Participant b						258.0 mL
Total Blood Volume per Panel E/G Titration Regimen 3 Participant b						312.0 mL

a If IV catheter use is necessary to support blood collection, additional blood (up to 2 mL per collection) may be collected and discarded prior to drawing the sample..

b If additional pharmacokinetic/pharmacodynamic and/or safety analysis is necessary, additional blood (up to 50 mL) may be obtained. Note: never to exceed 50 mL.

**10.9 Appendix 9: 12-Lead Electrocardiogram Abnormality Criteria (if criteria diverges from inclusion/exclusion criteria, more conservative criteria should be used)**

12-Lead Electrocardiogram Abnormality Criteria		
	Screen Failure Criteria	Potentially Significant Post Randomization Findings (clarification on action to take)
RHYTHM		
Sinus Tachycardia	>110 bpm	HR >110 bpm and HR increase of $\geq 25$ bpm from baseline
Sinus Bradycardia	<40 bpm	HR <40 bpm and HR decrease of $\geq 5$ bpm from baseline
Sinus Pause/Arrest	>2.0 seconds	>2.0 seconds
Atrial Premature Complex	>1 beat	$\geq 3$ beats
Ventricular Premature Complex	All	$\geq 3$ beats
Ectopic Atrial Rhythm	None	None
Junctional Rhythm	Junctional Rhythm with HR <40 bpm	Junctional Rhythm with HR <40 bpm
Idioventricular Rhythm	All	All
Atrial Fibrillation	All	All
Atrial Flutter	All	All
Supraventricular Tachycardia	All	All
Ventricular Tachycardia	All	All
AXIS		
Left Axis Deviation	RBBB With Left Anterior Hemiblock (LAHB)	New Onset LAHB
Right Axis Deviation	RBBB With Left Posterior Hemiblock (LPHB)	New Onset LPHB
CONDUCTION		
1st Degree AV Block	PR $\geq 230$ ms	PR $\geq 230$ ms + Increase of $>15$ ms; or PR Increase of $>25\%$
2nd Degree AV Block	Mobitz Type II	Mobitz Type II
3rd Degree AV Block	All	All
LBBB	All	All
RBBB	RBBB With LAHB/LPHB as Defined Above	New Onset RBBB (Not Including Rate-related)
Incomplete Right BBB (ICRBBB) (QRS <120 ms)	No Exclusion	Nothing
Short PR/ Preexcitation Syndrome	Delta Wave + PR <120 ms	Delta Wave + PR <120 ms

12-Lead Electrocardiogram Abnormality Criteria		
	Screen Failure Criteria	Potentially Significant Post Randomization Findings (clarification on action to take)
Other Intra-Ventricular Conduction Delay	QRS $\geq$ 130 ms	QRS $\geq$ 130 ms + Increase of $\geq$ 10 ms
QTc (B or F)		

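### Section 8 limits blood collection to 278 mL per participant by reference to Appendix 8, but Appendix 8 totals 297.5 mL for Panel D/F and 312.0 mL for Panel E/G Regimen 3 (300.0 mL once its PK count is corrected)

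*Combined protocol and SAP*

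**What the plan says.** Section 8 (Study Assessments and Procedures) sets a single limit for everyone: "The maximum amount of blood collected from each participant over the duration of the study will not exceed 278 mL (Appendix 8"). The same list allows repeat or unscheduled samples for safety or technical reasons.

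Appendix 8 (Section 10.8) builds the volumes by sample type. For Part 2 it prints 297.5 mL against "Total Blood Volume per Panel D/F Participant", 278.5 mL for Panel E/G Titration Regimen 1, 258.0 mL for Regimen 2, and 312.0 mL against "Total Blood Volume per Panel E/G Titration Regimen 3 Participant". One row, "Blood for MK-8189 and/or metabolites assay (Panel D/F and Panel E/G Titration Regimen 3"), gives both schedules 34 collections of 4.0 mL.

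Two footnotes to the Part 2 table matter:

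- Footnote a, on discard ahead of a sample, reads in part: "If IV catheter use is necessary to support blood collection, additional blood (up to 2 mL per collection) may be collected and discarded prior". This discard has its own flush rows and is included in the Part 2 totals.
- Footnote b, attached to the totals: "additional blood (up to 50 mL) may be obtained. Note: never to exceed 50 mL".

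Section 8.10.6 also allows up to 50 mL extra, then says that the total withdrawn will stay within a maximum allowable volume, again citing Appendix 8.

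The Regimen 3 Schedule of Activities (Section 1.3.5, footnote i) gives "Day 1 and Day 2: predose, 2, 6, 8, 10, 12 and 16 hours postdose", eight samples on Day 3 and ten on Day 9. It adds: "Optional sample when signs of dystonia and/or akathisia occur".

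**The concern.** A limit that cites a table should be at least as large as the largest total in that table. Here three of the four Part 2 totals are larger than the limit, two of them by far more than rounding could explain. A site that draws through a catheter with close to the full discard could follow the Schedule of Activities and Appendix 8 exactly and still break Section 8.

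Section 8.10.6 does not settle the matter, because Appendix 8 labels no figure as the maximum allowable volume. Nor do the documents say whether the extra 50 mL, the optional dystonia/akathisia sample or repeat samples count toward 278 mL.

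Separately, the Regimen 3 total is itself overstated, because its PK count disagrees with its own schedule.

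At stake is the accuracy of a per-participant limit in participants aged 61 to 80. The synopsis describes Part 1 as clinically complete, so the conflict concerns the panels still to be run or finished.

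**Working it through.** **Inputs** (Appendix 8, Part 2, unless stated)

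- Safety laboratory draws of 12.5 mL: 5 (D/F), 7 (Regimen 1), 6 (Regimens 2 and 3).
- HIV/hepatitis screen: 1 × 8.5 mL. Genetic sample: 1 × 8.5 mL. Together 17.0 mL and 2 draws.
- PK samples of 4.0 mL, as printed: 34 (D/F), 26 (Regimen 1), 25 (Regimen 2), 34 (Regimen 3).
- Catheter discard: up to 2.0 mL per draw.
- Limit: 278 mL (Section 8).

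**Step 1. Recount the PK samples from the Schedule of Activities footnotes**

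- D/F: 8 + 8 + 8 + 10 = 34, agrees.
- Regimen 1: 8 + 8 + 10 = 26, agrees.
- Regimen 2: 7 + 4 + 4 + 10 = 25, agrees.
- Regimen 3: 7 + 7 + 8 + 10 = 32; Appendix 8 has 34.

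**Step 2. Reproduce the printed totals**

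Base = labs × 12.5 + 17.0 + PK × 4.0. Draws = labs + 2 + PK. Total = base + 2 × draws.

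| Schedule | Base (mL) | Draws | Total with full discard (mL) | Printed (mL) | Against 278 |
|---|---|---|---|---|---|
| D/F | 62.5 + 17 + 136 = 215.5 | 41 | 297.5 | 297.5 | +19.5 |
| Regimen 1 | 87.5 + 17 + 104 = 208.5 | 35 | 278.5 | 278.5 | +0.5 |
| Regimen 2 | 75 + 17 + 100 = 192.0 | 33 | 258.0 | 258.0 | −20.0 |
| Regimen 3, 34 PK | 75 + 17 + 136 = 228.0 | 42 | 312.0 | 312.0 | +34.0 |
| Regimen 3, 32 PK | 75 + 17 + 128 = 220.0 | 40 | 300.0 | none | +22.0 |

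All four printed totals reproduce. Correcting the Regimen 3 count does not bring it under the limit, and D/F has no count to correct.

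**Step 3. How much discard is needed to cross 278 mL?**

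With no discard the base volumes apply, and all are within the limit.

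With full discard on PK draws only (base + 2 × PK):

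- D/F: 215.5 + 68 = 283.5 (+5.5).
- Regimen 1: 208.5 + 52 = 260.5 (−17.5).
- Regimen 2: 192.0 + 50 = 242.0 (−36.0).
- Regimen 3 corrected: 220.0 + 64 = 284.0 (+6.0).

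The break-even mean discard per draw is (278 − base) / draws:

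- D/F: 62.5/41 = 1.52 mL over all draws, or 62.5/34 = 1.84 mL over PK draws only.
- Regimen 3 corrected: 58/40 = 1.45 mL, or 58/32 = 1.81 mL.

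**Step 4. If the extra 50 mL is drawn in full and counts toward the limit**

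In the order D/F, Regimens 1, 2 and 3 (corrected):

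- No discard: 265.5, 258.5, 242.0, 270.0 mL. All fit.
- Full discard on PK draws only: 333.5, 310.5, 292.0, 334.0 mL. None fits.

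**The case against.** The best defence is that 278 mL was never meant to include discarded blood. The printed Regimen 3 volume without discard plus the 50 mL allowance is 228.0 + 50 = 278.0 mL exactly, so the limit may be a ceiling on study samples that was not updated when discard was added. That is plausible, but it is an inference, and the text points the other way. Footnote a describes the discard as collected, Section 8 limits blood collected, Section 8.10.6 limits blood withdrawn, and the Part 2 totals include the flush rows. As evidence of intent only, the Amendment 02 rationale in the Document History says the maximum was changed to allow for discarded blood. The derivation also depends on the miscounted row: with 32 samples it gives 220.0 + 50 = 270.0 mL.

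A second objection concerns practical reach, and much of it stands. Discard applies only if a catheter is needed, and 2 mL is its upper end. At the full 2 mL, D/F crosses the limit only at the 32nd discard draw of 41 (62.5/2 = 31.25), and corrected Regimen 3 at the 30th of 40 (58/2 = 29). Suppose, as an assumption the documents neither state nor exclude, that catheters cover only the predose to 16-hour PK draws, 28 in either schedule. Full discard then gives 215.5 + 56 = 271.5 mL and 220.0 + 56 = 276.0 mL, both within the limit. On PK draws alone, an excess therefore also needs discard at some of the 24-, 36- or 48-hour samples.

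Third, Regimen 3 may never be used, since Panel E/G starts with one selected regimen and moves to another only if tolerability is poor. The exposure that does not depend on regimen choice is Panel D/F.

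These points limit how often the excess would occur. They do not make Section 8 agree with the table it cites.

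**Conclusion.** The concern holds. Panel D/F is the firmest case: its PK count is right, its total reproduces, and it is 19.5 mL over the limit (19.5/278 = 7.0%) with full discard on every draw, or 5.5 mL over (2.0%) with full discard on PK draws only. Regimen 3, once corrected, is 22.0 mL or 6.0 mL over on the same two assumptions. Regimen 1 exceeds by 0.5 mL, which may be rounding, and Regimen 2 fits.

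The full-discard totals are upper bounds for the scheduled draws only; the extra 50 mL and any optional or repeat samples would come on top. The conclusion assumes that discarded blood counts as collected, which is how Appendix 8 treats it in Part 2. It makes no claim about which limit is right. It should be fixed because a stated per-participant limit is contradicted by its own source.

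**What to change.** 1. In Appendix 8, separate Regimen 3 from Panel D/F in the PK row and correct it: collections 34 to 32 (136.0 to 128.0 mL), flush 42 to 40 (84.0 to 80.0 mL), total 312.0 to 300.0 mL.
2. Reconcile Section 8, Section 8.10.6 and Appendix 8 to one maximum, labelled as such in Appendix 8. State whether catheter discard, the extra 50 mL, the optional dystonia/akathisia sample and repeat samples count toward it. Align Section 8.3 as well: it sends the reader to Section 8 for volumes by visit and sample type, but the volume table is in Appendix 8.
3. If 278 mL is the approved limit, reconcile the Panel D/F and Panel E/G schedules or the discard allowance to it.
4. For the record only, since Part 1 is clinically complete: Panel C also shows 34 PK samples against 7 + 7 + 8 + 10 = 32 in its schedule (Section 1.3.1, footnote j) and has no flush row.

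Items 1, 2 and 4 are text and table corrections for the next amendment, with the same figure carried to the consent form if it states one; they add no procedures. Item 3 would cost more, because it could change sampling or discard.

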## **8.1 Administrative and General Procedures**

### **8.1.1 Informed Consent**

The investigator or medically qualified designee (consistent with local requirements) must obtain documented consent from each potential participant or each participant's legally acceptable representative prior to participating in a clinical study or future biomedical research. If there are changes to the participant's status during the study (eg, health or age of majority requirements), the investigator or medically qualified designee must ensure the appropriate consent is in place.

#### **8.1.1.1 General Informed Consent**

Consent must be documented by the participant's dated signature or by the participant's legally acceptable representative's dated signature on a consent form along with the dated signature of the person conducting the consent discussion.

A copy of the signed and dated consent form should be given to the participant before participation in the study.

The initial ICF, any subsequent revised written ICF, and any written information provided to the participant must receive the IRB/IEC's approval/favorable opinion in advance of use. The participant or his/her legally acceptable representative should be informed in a timely manner if new information becomes available that may be relevant to the participant's willingness to continue participation in the study. The communication of this information will be provided and documented via a revised consent form or addendum to the original consent form that captures the participant's dated signature or by the participant's legally acceptable representative's dated signature.

Specifics about a study and the study population will be added to the consent form template at the protocol level.

The informed consent will adhere to IRB/IEC requirements, applicable laws and regulations, and Sponsor requirements.

